2.2 Secondary Objectives

2.21 To evaluate acute and late toxicity
2.22 To estimate the 5-year locoregional control, invasive disease-free survival and overall survival.

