13.0 Treatment/Follow-up Decision at Evaluation of Patient

Follow-up data will be collected and entered after the observation phase outlined in section 4.0. If the patient is still alive after 5 years have elapsed from the on-study date, no further follow-up is required by this protocol.

- 13.1 Patients who have a recurrence while receiving therapy or during observation will go to the event-monitoring phase and be followed
- 13.2 Patients who discontinue treatment or observation for reasons other than recurrence will go to the event-monitoring phase and be followed
- 13.3 Patients who will not receive any radiation treatment or who will receive radiation treatment elsewhere will move to event monitoring phase.
- 13.4 A patient is deemed *ineligible* if after registration, it is determined that at the time of registration, the patient did not satisfy each and every eligibility criteria for study entry. The patient may continue treatment off-protocol at the discretion of the physician as long as there are no safety concerns, and the patient was properly registered. The patient will go directly to the event-monitoring phase of the study (or off study, if applicable).

If the patient received treatment, all data up until the point of confirmation of ineligibility must be submitted. Event monitoring will be required per Section 18.0 of the protocol.

If the patient never received treatment, on-study material and the End of Active Treatment/Cancel Notification Form must be submitted. No further data submission is necessary.

- 13.5 A patient is deemed *withdrawn* if she is removed from the study for any reason before any study treatment is given. On-study material and the End of Active Treatment/Cancel Notification Form must be submitted. No further data submission is necessary.

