16.0 Statistical Considerations and Methodology

- 16.1 Overview: This is an open label phase III randomized controlled trial to determine the safety of 5 fraction vs 15 fraction radiotherapy after breast conserving surgery. The goal is to determine whether the difference in 24-month complication rates between the experimental arm and the control arm is acceptable. Of interest is whether the experimental arm results in an unacceptable increase in the 24-month complication rate. If it does not, then the experimental arm will be recommended for further study. If the 24-month complication rate is found to be unacceptable, then the recommendation would be to do no further studies of the experimental arm.

- 16.2 Primary and Secondary Endpoints

16.21 Primary Endpoint: The 24-month complication rate, defined as the percentage of women evaluable at 24 months who develop one or more of the following events:

- 1) grade 3 or higher late adverse event OR
- 2) deterioration of cosmesis from excellent/good to fair/poor or from fair to poor at the 24-month evaluation (using the Harvard/NSABP/RTOG Cosmesis Scale)

16.22 Secondary Endpoints:

16.221 Acute and late adverse events including grade ≥ 2 pneumonitis.

16.223 Locoregional control, invasive disease-free, distant recurrence, disease-free survival, cause-specific survival, overall survival.

The following definitions are used for the secondary endpoints of interest:

- *Acute adverse events*: any adverse event, regardless of attribution, that occurs in the first 90 days post-RT.
- *Late adverse events* (up to 5 years post RT): any adverse event that occurred after the first 90 days post-RT and up to 5 years post-RT.
- *Ipsilateral breast tumor recurrence (IBTR)*: this is defined as local recurrence from trial registration as a first event at 5 years. IBTR is defined as both invasive and non-invasive breast cancer involving the same breast parenchyma as the original tumor.
- *Regional recurrence*: invasive breast cancer in the axilla, regional lymph nodes, chest wall, and skin of the ipsilateral breast at 5 years.
- *Distant recurrence*: metastatic cancer that has either been biopsy confirmed or clinically diagnosed as recurrent invasive breast cancer at 5 years.

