16.62 Secondary Analyses

16.621 *Acute adverse events:* All patients who were registered to the study and started treatment will be included in the acute adverse event analysis. An acute adverse event is an AE, regardless of attribution, that occurs up to 90 days post-RT. The maximum grade for each type of acute AE will be recorded for each patient. Data will be summarized as frequencies and relative frequencies by treatment arm. Additionally, the relationship of the adverse event(s) to the study treatment will be taken into consideration. Rates will be compared between arms using chi-squared tests.

16.622 *Late adverse events:* All patients who were registered to the study and started treatment will be included in the late adverse event analysis. A late adverse event is an AE, regardless of attribution, that appears or persists after 90 days post-RT and up to 5 years post-RT. The maximum grade for each type of late AE will be recorded for each patient. Data will be summarized as frequencies and relative frequencies by treatment arm. Additionally, the relationship of the adverse event(s) to the study treatment will be taken into consideration. Rates will be compared between arms using chi-squared tests.

16.623 *Locoregional control:* The cumulative incidence of locoregional recurrence will be estimated using a competing risks method (Gooley et al.) by treatment arm. The competing risks will be distant breast cancer recurrence and death. Comparison between arms will employ Fine-Gray regression.

16.624 *Invasive disease-free survival:* i-DFS is defined as the time from registration until the time of invasive disease recurrence (not including DCIS) or death due to any cause. The i-DFS will be estimated with a Kaplan-Meier estimator and curve by treatment arm. Estimates will be given for specific time points along with 95% CIs. Comparison between arms will employ a log-rank test.

16.625 *Disease-free survival:* DFS is defined as the time from registration until the time of disease recurrence or death due to any cause. The DFS will be estimated with a Kaplan-Meier estimator and curve by treatment arm. Estimates will be given for specific time points along with 95% CIs. Comparison between arms will employ a log-rank test.

16.626 *Cause specific survival:* The CSS will be estimated with a Kaplan-Meier estimator and curve by treatment arm. Estimates will be given for specific time

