16.7 Data & Safety Monitoring

16.71 The study chair(s) and the study statistician will review the study at least twice a year to identify accrual, adverse event, and any endpoint problems that might be developing. The Mayo Clinic Cancer Center (MCCC) Data Safety Monitoring Board (DSMB) is responsible for reviewing accrual and safety data for this trial at least twice a year, based on reports provided by the MCCC Statistical Office.

16.72 Adverse Event Stopping Rules: The stopping rules specified below are based on knowledge available at study development. We note that the Adverse Event Stopping Rule may be adjusted in the event of either (1) the study re-opening to accrual or (2) at any time during the conduct of the trial and in consideration of newly acquired information regarding the adverse event profile of the treatment(s) under investigation. The study team may choose to suspend accrual because of unexpected adverse event profiles that have not crossed the specified rule below.

Accrual will be temporarily suspended if at any time we observe events considered at least possibly related to study treatment (i.e. an adverse event with attribute specified as “possible,” “probable,” or “definite”) that satisfy one of the following:

- If 4 or more patients in the first 10 treated patients (per treatment arm) experience a grade 3 or higher adverse event, besides acute dermatitis, at least possibly related to treatment at any time following completion of the protocol treatment within 90 days post-treatment.
- After the first 10 patients have been treated (per treatment arm): if $\geq 20\%$ of all patients experience a grade 3 or higher adverse event, besides acute

dermatitis, at least possibly related to treatment at any time following the completion of protocol treatment within 90 days post-treatment.

We note that we will review grade 4 and 5 adverse events deemed “unrelated” or “unlikely to be related”, to verify their attribution and to monitor the emergence of a previously unrecognized treatment-related adverse event.

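### The accrual-suspension rule in 16.72 counts grade 3+ events only after treatment is completed, and 16.22 and 16.621 disagree on when the acute window starts

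*Combined protocol and SAP*

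**What the plan says.** **Suspension rule (protocol 16.72).** The first trigger reads "If 4 or more patients in the first 10 treated patients (per treatment arm) experience a grade 3 or higher adverse event", with acute dermatitis exempted, and the event must be "at least possibly related to treatment at any time following completion of the protocol treatment within 90 days post-treatment". The second trigger applies once ten patients per arm have been treated. It fires at 20% or more of all patients and uses the same window in almost the same words. The section also leaves room for judgement: "The study team may choose to suspend accrual because of unexpected adverse event profiles that have not crossed the specified rule below".

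**Acute adverse events.** The endpoint definitions in 16.22 describe an acute event as "any adverse event, regardless of attribution, that occurs in the first 90 days post-RT". The analysis text in 16.621 says: "An acute adverse event is an AE, regardless of attribution, that occurs up to 90 days post-RT". The first has a start and an end; the second has only an end. On the population, 16.621 says: "All patients who were registered to the study and started treatment will be included in the acute adverse event analysis". The comparison serves secondary objective 2.21, "To evaluate acute and late toxicity".

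**Early stoppers.** Section 13.2 says: "Patients who discontinue treatment or observation for reasons other than recurrence will go to the event-monitoring phase and be followed".

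**The concern.** A toxicity rule normally counts from first exposure. This one opens its window at completion of protocol treatment, so two kinds of event cannot reach it:

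- a grade 3+ event that begins and resolves while radiotherapy is still being given;
- a grade 3+ event in a woman whose treatment ends because of it, since she has no completion date.

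The second case makes the rule internally inconsistent. The denominators are treated patients and all patients, so she is counted below the line but cannot be counted above it.

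The two acute definitions add a separate problem. They can give different numerators for the same chi-squared comparison. Because the schedules differ in length by design, the time in dispute is longer in the control arm. At stake are a prespecified safety trigger in an open-label trial whose stated aim is safety, and the clarity of one secondary comparison.

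**Working it through.** **1. The plan's own figures.** 16.72 gives no operating characteristics for the suspension rule, so there is nothing to reproduce there. The plan's computed figure is the sample size in 16.4 and 16.5: 50 evaluable per arm, 10% in both arms, margin 15 points, one-sided alpha 0.05. The standard error is √(2 × 0.10 × 0.90 / 50) = √0.0036 = 0.06. Power is Φ(0.15/0.06 − 1.645) = Φ(0.855) = 80.4%. This reproduces the stated 80%. It concerns the 24-month endpoint and does not bear on this point.

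**2. The texts side by side, read literally** (grade 3+, not acute dermatitis, at least possibly related)

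| Event | 16.72 | 16.22 | 16.621 |
|---|---|---|---|
| Starts and resolves during radiotherapy | not counted | neither acute nor late | acute |
| Starts during radiotherapy, still present after completion | can count | can count as acute | acute |
| Starts within 90 days after completion | counts | acute | acute |
| Occurs in a woman who stops early | no window | depends on how the end of RT is read | in the analysis population |

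The late definition does not rescue the first row. 16.22 requires occurrence after the first 90 days, and 16.622 requires the event to appear or persist beyond that point.

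**3. How long the affected period is.** Inputs:

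- Arm 1: 15 fractions (7.311). The optional sequential boost adds 10/2.5 = 4, giving 19 (7.312). An integrated boost stays within 15.
- Arm 2: 5 daily fractions (7.2 and 7.321).
- Arm 1's fractions per week are not stated. I assume 5, which matches the 3 weeks that section 1.3 gives for the 15-fraction trial on which the control arm is based.

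Calendar span = fractions + 2 × weekends crossed:

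| Schedule | Shortest | Longest |
|---|---|---|
| Arm 1, 15 fractions | 15 + 4 = 19 days (Monday start) | 15 + 6 = 21 days |
| Arm 1, 19 fractions | 19 + 6 = 25 days (Monday or Tuesday start) | 19 + 8 = 27 days |
| Arm 2, 5 fractions | 5 days (Monday start) | 5 + 2 = 7 days |

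For the same start day, the Arm 1 to Arm 2 ratio runs from 21/7 = 3.0 to 25/5 = 5.0. As a share of the time from first fraction to 90 days post-treatment, T/(T + 90), the period is 19/109 = 17% to 27/117 = 23% in Arm 1, and 5/95 = 5% to 7/97 = 7% in Arm 2. These are shares of days, not of events.

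**4. What uncounted events would do to the first trigger (illustration only).** Let p be the true per-patient rate of a qualifying event and s the share of affected patients whose events all go uncounted. Both are assumptions. P(suspend) = P(X ≥ 4) with X ~ Binomial(10, p(1 − s)):

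| p | s = 0 | s = 0.10 | s = 0.25 | s = 0.50 |
|---|---|---|---|---|
| 0.10 | 1.3% | 0.9% | 0.5% | 0.1% |
| 0.20 | 12.1% | 8.8% | 5.0% | 1.3% |
| 0.40 | 61.8% | 51.3% | 35.0% | 12.1% |

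For the second trigger, take one look at 20 patients in an arm (4 or more needed) and p = 0.20. The chances are 58.9%, 49.7%, 35.2% and 13.3% across the same values of s. The omission matters when toxicity is high enough for the rule to be needed. It matters little when events are rare.

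**The case against.** The strongest reply is that on-treatment toxicity is not unmonitored. Section 10.5 requires grade 3-5 events outside the solicited list to be submitted whatever their attribution. Section 18.1 lists adverse event forms at end of treatment. The study team and the safety board each review the trial at least twice a year, and 16.72 lets the team suspend accrual without a trigger. All of that stands and limits the consequence. It does not mend the trigger itself: discretion is not a prespecified rule.

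A second reply is that few events are affected. Acute dermatitis is exempt whatever its timing, and an event that outlasts treatment can still count. Section 1.4 reports very low grade 3 rates for similar schedules, and at such rates neither trigger is likely to be met under either window. This also stands, and it is why no effect on event counts is claimed.

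Several stronger readings are tempting but not supported:

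- *A reader might infer that the acute analysis as a whole leaves out on-treatment events and women who do not finish.* Only 16.22 starts at the end of radiotherapy. 16.621 sets no start and takes in everyone who began treatment. The acute defect is a conflict between two sections.
- *A reader might infer that the same reaction on day 16 is excluded in Arm 1 and counted in Arm 2.* That requires it to resolve before the last Arm 1 fraction and, under 16.72, not to be dermatitis.
- *A reader might infer that the calendar shares show how many events are lost.* The documents give no on-treatment grade 3+ rate for this population, so days cannot be converted to events.

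**Conclusion.** The point holds in two limited parts.

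1. As written, both bullets of 16.72 cannot count a grade 3+ event confined to the treatment period. They also give no counting window to a woman who stops early, although she is in the denominator. This rests on the literal wording alone.
2. 16.22 and 16.621 conflict on an event confined to treatment: neither acute nor late under the first, acute under the second.

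The period affected is 19-27 days in Arm 1 and 5-7 days in Arm 2, if treatment runs at 5 fractions per week. The effect on event numbers is unknown, and the binomial figures only show direction. The primary endpoint is unaffected, because its adverse event component is late toxicity and its other component is cosmesis at 24 months. This should be corrected as a matter of safety-rule wording; it does not threaten the trial's main conclusion.

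**What to change.** Use one window in both bullets of 16.72, and use it to reconcile 16.22 with 16.621: *from the first fraction through 90 days after the last fraction received, whether or not the planned course was completed.* Leave the thresholds and the dermatitis exemption as they are.

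Costs:

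- Reported acute rates will be slightly higher, and the suspension rule slightly more likely to trigger.
- The window becomes 109-117 days in Arm 1 and 95-97 days in Arm 2, so it is about 12 (19 − 7) to 22 (27 − 5) days longer in Arm 1. This should be stated wherever the arms are compared.
- Data collection needs a check. Adverse event forms are already due at end of treatment, but early stoppers move to event monitoring. In the section 18.1 table as it can be read, only the patient status form is marked for that phase. Footnote 8 in section 4.0 also leaves some end-of-treatment assessments in Arm 2 to discretion; the row labels are not legible enough to say which. The plan should confirm that adverse events are graded for early stoppers through the 90 days.

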4.0 Test Schedule

	Baseline	Pre-treatment	EOT	Observation ¹²			
	≤120 days prior to start of treatment	≤45 days prior to start of treatment ⁶	Last day of Treatment (+/- 5 days)	12 weeks (+/- 4 weeks) post-treatment	6 months (+/- 2 months)	12 months (+/- 3 months), 24 months (+/- 6 months), 36 months (+/- 6 months), 48 months (+/- 6 months) and 5 years (+/- 6 months) post completion of treatment	Failure*
Consent	X						
Physical exam ¹	X						
Exam/ECOG							
Visit (see Appendix)	X		X ⁸	X		X	X
Visit (see Section)		X ⁹	X ⁸	X		X ¹³	X
Visit ³		X	X	X		X	
Visit (sites 2,3,4) ¹¹		X ⁹	X	X	X	X	X
Visit (see)		X ⁹	X	X		X	X
Specimens							
Initial specimen	X ⁵						X ²
							X ⁷

1. A general history & physical exam should include height and weight (optional at Rochester site)
2. Review of pathology at failure if obtained clinically
3. Photographs can be done at any time before or after treatment at the discretion of the physician
4. Last day of treatment +/- 2 days per discretion of treating physician
5. Outside pathology must be reviewed at treating institution to confirm eligibility within 365 days.
6. Blood pregnancy test to be completed prior to start of treatment on day 1 (for women of childbearing potential only).
7. PET Scan at failure optional
8. Per discretion of treating physician for Arm 2 (5 days)
9. These tests can be done before or up to 3 days into treatment
10. Limited physical exam to include ECOG; weight (optional for Rochester site)
11. As collected clinically
12. Patients that cannot come back to Mayo within the time constraints of the follow-up schedule; efforts to obtain outside records and complete QOL's will occur, however the required items may not be captured.
13. If follow up visit occurred at an outside institution, Cosmetic Assessment will not be required.

*Failure defined as recurrent disease

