16.8 Results Reporting on ClinicalTrials.gov: At study activation, this study will have been registered within the “ClinicalTrials.gov” website. The Primary and Secondary Endpoints (i.e., “Outcome Measures”) along with other required information for this study will be reported on ClinicalTrials.gov. For purposes of timing of the Results Reporting, the initial estimated completion date for the Primary Endpoint of this study is 48 months after the study opens to accrual. The definition of “Primary Endpoint Completion Date” (PECD) for this study is at the time the last patient registered has been observed for 24 months.

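### The running 20% accrual-suspension rule counts women still inside the 90-day event window as event-free, so it understates the 90-day toxicity rate while accrual is open

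*Combined protocol and SAP*

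**What the plan says.** Section 16.72 gives two triggers for related grade 3 or higher events other than acute dermatitis. Both are checked continuously: "Accrual will be temporarily suspended if at any time we observe events" that meet either one.

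- First bullet, a fixed count: "If 4 or more patients in the first 10 treated patients (per treatment arm") have such an event.
- Second bullet, a running proportion: "After the first 10 patients have been treated (per treatment arm"), at least 20% "of all patients experience a grade 3 or higher adverse event, besides acute" dermatitis, the event being "at least possibly related to treatment at any time following the completion of protocol treatment within 90 days post-treatment".

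The second bullet starts on patients treated, not on patients followed. No evaluable set is defined for it here or elsewhere. Accrual does not pause after the tenth patient, and no operating characteristics are given for either bullet.

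Section 10.4 has adverse events graded at each evaluation. Section 18.1 lists adverse event forms at end of treatment and then at the 12-week/observation visits. Section 4.0 places the first visit after end of treatment at "12 weeks (+/- 4 weeks) post-treatment", that is, days 56 to 112.

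**The concern.** The numerator is a 90-day cumulative event count. The denominator includes women who have had only part of those 90 days, or almost none. Each such woman adds a full unit below the line but can contribute only the events that have happened and become known so far. The proportion compared with 20% is therefore not the 90-day rate that the rule is written around; in expectation it is lower.

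Under steady accrual the number of women inside the window stays roughly constant while the total treated grows. The dilution is then greatest soon after the tenth patient, when a suspension would spare the most women. It would be less concentrated at the start if accrual began slowly and then sped up.

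It does not matter whether the 20% is taken per arm or over both arms, which the bullet leaves open: both readings include women with incomplete follow-up. The fixed count in the first bullet has no growing denominator and is not diluted in this way.

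**Working it through.** **The plan's own figure.** None is stated for this rule. The nearest design figure, Section 16.5's 80% power with 50 evaluable per arm, does reproduce: SE = √(2 × 0.10 × 0.90 / 50) = 0.06, and power = Φ(0.15/0.06 − 1.645) = 80.4%. It has no bearing on the suspension rule.

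**Inputs**

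- 55 women per arm (Section 5.1).
- Accrual period: Section 16.8 says "the initial estimated completion date for the Primary Endpoint of this study is 48 months after the study opens to accrual" and defines completion as the last patient observed for 24 months. So accrual is about 48 − 24 = 24 months. This is derived, not stated; 12 and 36 months are assumed as a range.
- Accrual rate L = 55/24 = 2.29 per arm per month, or one woman about every 13.3 days.
- Event timing is not given. Two bounding assumptions: (a) events spread evenly over 90 days and known at once; (b) events known only at a visit on day 84.

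**Women still inside the window.** Share = min(n, L × window)/n. With a 90-day window, L × window = 6.8 women per arm.

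| Treated per arm | 12-month accrual | 24-month | 36-month |
|---|---|---|---|
| 11 | 100% | 62% | 41% |
| 20 | 68% | 34% | 23% |
| 55 | 25% | 12% | 8% |

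**Expected observed rate divided by true rate.** Average, over the n treated women, the probability that an event is already known. With 24 months of accrual and 11 treated, follow-up times are 0, 13.3, 26.6, … days.

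- (b) Four of the 11 are past day 84: 4/11 = 0.36.
- (a) Those four count fully. The other seven contribute (0+1+…+6) × 13.3/90 = 3.1. So (4 + 3.1)/11 = 0.65.

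| Treated per arm | (a) known at once | (b) known at visit | True rate for an expected observed 20%, 0.20/ratio |
|---|---|---|---|
| 11 | 0.65 | 0.36 | 31% to 55% |
| 20 | 0.80 | 0.65 | 25% to 31% |
| 55 | 0.93 | 0.87 | 22% to 23% |

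The last column describes the expectation at a single look. It is not the rule's actual trigger point, because the rule is checked repeatedly.

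**Chance that accrual is ever suspended.** Simulation of one arm: Poisson accrual at 2.29 per month, 5-day treatment, checks at every start, event and follow-up completion until the 55th woman starts, and the current trigger active from the 11th woman treated. The amended rule is the current trigger plus the clause under fix. Ranges span (a) and (b), with visits in (b) varying over the 8-to-16-week window; repeat runs move by a point or two.

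| True 90-day rate | Current | Amended, from 11 completed |
|---|---|---|
| 5% | 1-2% | 4-7% |
| 10% | 10-14% | 21-32% |
| 20% | 61-72% | 80-86% |
| 25% | 85-91% | 94-97% |

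**The case against.** Four points on the other side deserve weight.

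1. **Events need not wait for the visit.** Section 10.5 requires grade 3 to 5 events outside the solicited list to be submitted, and Section 10.3 has the team act when an event is identified. A reader might infer that every look understates the rate by 13% to 65%, or that a true rate above 55% is needed just after the tenth patient. The documents do not support either as a central figure: they hold only if no event is known before week 12. With events known at once, the figure at 11 treated is 31%. The downward direction remains under both assumptions.

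2. **Repeated looks offset some of the dilution.** A reader might infer that the rule cannot catch a toxic regimen. It can: at a true 30% rate the present bullet fires in 96-98% of simulated trials, at a median of 13 to 17 treated per arm. The loss lies mainly around 20-25%, and in how early the rule fires.

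3. **There are backstops.** Section 16.7 provides review at least twice a year by the study chair and statistician and by the DSMB, allows the team to suspend accrual without the rule being crossed, and allows the rule to be adjusted. These reduce the consequence. They do not correct the pre-specified quantitative trigger. The first bullet does not fill the gap either, since 4 of 10 is an observed rate of 40%.

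4. **Simply replacing the denominator would do harm.** If the rule waited for 10 completed women, then at a true 40% rate it would fire at a median of 17 treated, against 11 to 14 now. It would also fire on 2 of 10. This objection stands and shapes the fix.

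**Conclusion.** The point holds. On the plain reading of Section 16.72, women with incomplete 90-day follow-up are in the denominator, and no other section removes them. The observed rate is biased downward for as long as accrual is open. That direction does not depend on the accrual rate or on event timing.

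The size does. Under an inferred 24-month, roughly constant accrual, the expected observed rate at 20 treated per arm is 65% to 80% of the true rate, and at 55 treated 87% to 93%. At 20 treated, the share of women still inside the window runs from 23% to 68% as accrual goes from 36 to 12 months. The practical loss is a chance of suspension at a true 20% rate of 61-72%, where a rule that also looks at completed follow-up reaches 80-86%.

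This is a worthwhile, inexpensive correction to a monitoring rule. It is not evidence that the trial lacks safety oversight, and it does not question the 20% threshold, which is the sponsor's choice.

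**What to change.** Keep the second bullet and add a clause such as:

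> or, once at least 11 patients in an arm have completed the 90-day window/12-week AE assessment, if at least 20% of the patients in that arm who have completed it or have already had a qualifying event experienced such an event.

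The plan should name which of the two marks completion. The visit may fall on day 56, 34 days before the window closes, or on day 112, after it has closed. The simulated ranges cover both: 90 days elapsed in (a), visit done in (b). The plan should also say whether the existing percentage is per arm or pooled, and state the operating characteristics of the amended rule.

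Because the present trigger stays, the amended rule can never fire later than the present one, including for very toxic regimens. Counting a woman with an early event at once pushes the new proportion slightly upward.

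**Cost.** One sentence and no new data. There will be more temporary suspensions at lower true rates: 4-7% against 1-2% per arm at a true 5%, and 21-32% against 10-14% at a true 10%. If both arms had a true 5% rate and were treated as independent, the upper figures imply a suspension in at least one arm in 1 − 0.93² = 14% of trials, against 1 − 0.98² = 4% now. Starting at 10 completed women rather than 11 should be avoided: 2 of 10 would then trigger, against 3 of 11, and the figure at a true 5% rises to about 9-12% per arm.
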